2 OBJECTIVES AND ENDPOINTS

2.1 Primary Objective

To evaluate whether, a group of heart failure patients who are not currently targeted for pacing therapy for heart failure, will obtain benefit from pacing therapy delivered to allow optimisation of LV preload by shortening Atrioventricular delay.

2.2 Secondary Objective

To assess direct His pacing characteristics in this population (including acute and chronic pacing thresholds).

2.3 **Primary Endpoint**

The primary outcome measure will be exercise capacity, measured using peak oxygen uptake (VO₂).

2.4 Secondary Endpoints

Secondary outcome measures are:

- (1) Echocardiographic measurement of left ventricular function and remodelling
- (2) Changes in B-type Naturietic Peptide (BNP)
- (3) Changes in Quality of Life Scores
- (4) Changes in daily activity levels recorded using objective metrics from the pacemaker device
- (5) Cost effectiveness analysis
- (6) Percentage pacing will be recorded, as will arrhythmia burden (atrial fibrillation, atrial flutter and ventricular arrhythmias), pacing thresholds, R wave amplitude and lead impedance. Fluoroscopy time during device insertion will also be reported.

3 STUDY DESIGN

3.1 Design

This is a multi-centre, prospective randomised double-blinded cross over study, recruiting a sub-population of patients with heart failure from multiple investigational sites in the UK. Recruitment is expected to take place over about 2 years.

All patients will be implanted with a Pacemaker or Implantable Cardioverter Defibrillator with one of the leads positioned on the His bundle in order to obtain His-bundle capture. There will be a 2-month run-in period where the device will be programmed not to deliver His pacing therapy during this period. Patients will be allocated in random order to six month treatment periods in each of the following two states (1) No His bundle pacing; (2) AV optimised Hisbundle pacing. Endpoint measurements will be taken at baseline, 6 months and 12 months post randomisation. Treatment allocation will be blinded to the endpoint assessor.

3.2 Treatment regimens

Treatment regimens are summarised in the flow diagram in Appendix 1.

4 PARTICIPANT ENTRY

4.1 Study population

(i) Inclusion criteria

- 1. Aged 18 or above
- 2. *Ventricular Ejection Fraction (EF) ≤ 40%; BNP needs to be ≥250ng/L for patients with EF 36-40%,
- 3. New York Heart Association (NYHA) class II-IV
- 4. **PR interval ≥200ms
- 5. **Narrow QRS duration (≤140ms) or prolonged QRS duration with typical Right Bundle Branch Block (RBBB) morphology on 12 lead ECG and sinus rhythm

* Ejection Fraction should be based on patient's echocardiograph within the last 18 months; if that is not available a new echo will be performed. Patients with EF 36-40% must have at least one BNP result within the last 18 months having a value of \geq 250ng/L, otherwise, a blood test will be done to assess BNP. Some centres use NT-pro BNP test instead of BNP. An NT-pro BNP result of \geq 600ng/L is acceptable.

** ECG criteria should be based on patient's ECG within the last 18 months; if that is not available a new ECG will be performed.

(ii) Exclusion criteria

- 1 ***Permanent or persistent atrial fibrillation (AF)
- 2 Paroxysmal atrial fibrillation with history of sustained AF (more than 24 hours) in the 6 months prior to screening
- 3 Patients who are unable to perform cardiopulmonary exercise testing
- 4 Other serious medical condition with life expectancy of less than 1 year
- 5 Lack of capacity to consent

HOPE-HF Sponsor: Imperial College (study ref: 15HH2828)

- 6 Pregnancy (female participants of reproductive age will be eligible for inclusion in the study, subject to a negative pregnancy test prior to randomisation)
- 7 Contraindication to use of the relevant study device or leads (as per current manuals from manufacturer)

***Patients who have persistent AF in their medical history but has then resolved can be included.

Eligible patients can be sub-divided into 2 groups: A) patients who do not have an indication for an implantable ICD (this group will receive His CRT-P); and B) patients who do have an indication for an implantable ICD (this cohort will receive His CRT-D)

Patients who meet the study inclusion criteria, but have completed other research studies or concurrently participating in a non-interventional study (e.g. observational studies) may be invited to take part in the trial at the Investigator's discretion.

5 PROCEDURES AND MEASUREMENTS

5.1 Screening and pre-randomisation evaluations

Written informed consent will be obtained before the subject undergoes any screening procedures.

Potential study participants will be identified following the review of medical notes of patients attending; general cardiology clinics, Heart Failure clinics, ICD clinics or during admission to hospital. Patients who potentially fulfil the study inclusion criteria and none of the exclusion criteria will be identified and approached by members of their direct healthcare team to discuss study participation.

All subjects will be assigned a study-specific subject number at the screening visit and the following tests/assessments will be performed:

- 1. ECG (can be taken at the visit or within the past 18 months; this ECG determines patient eligibility and will be reviewed centrally)
- 2. Echocardiography (new echo will be performed if no report is available within the past 18 months)
- 3. BNP or NTproBNP in some centres (sample is only taken for patients with EF 36-40% and have no available BNP result within the past 18 months).
- 4. Demographics
- 5. Medical History
- 6. Physical Examination
- 7. Pregnancy test will be performed for women of childbearing age

Eligible patients will be asked to complete a resource utilisation questionnaire at this visit.

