5.3 Treatment

Patients entering the study will then attend for implantation of their device, this will be performed either at their local hospital or at Imperial College NHS Healthcare Trust, no later than 4 months of the patient's screening visit

Prior to implantation, blood tests will be performed to assess clotting function, full blood count and electrolytes. Additionally, blood will be taken for group and save if required as per local clinical practice. Antibiotic prophylaxis, analgesia and sedation can all be given as per the implanting institution's local policies and normal practice. As is standard clinical practice for pacemaker implantation, the following routine blood tests will be performed: creatinine level, haemoglobin level, prothrombin time (PT; clotting), and Group and Save (G+S). Tests performed up to a specified date prior to the implantation day can be accepted, please refer to Appendix 2 for details.

All patients will be implanted with a Pacemaker or Implantable cardioverter defibrillator (ICD). In all patients, a pacing lead will be positioned in the right atrium (typically the right atrial appendage). All patients will have a pacemaker lead positioned on the His bundle in order to obtain His-bundle capture. If it is not possible to successfully implant a His-bundle lead with selective His bundle capture or non-selective capture with < 40ms prolongation of the QRS duration, then a lead will be implanted in a lateral branch of the coronary sinus.

In patients who do not have an indication for an Implantable cardioverter defibrillator (ICD), a second ventricular lead will be implanted in a lateral branch of the coronary sinus. If His pacing has not been successfully achieved then a further lead will be positioned at the RV apex. In patients who do have an indication for an Implantable cardioverter defibrillator, the ICD lead will be positioned in the right ventricle (either RV apex or RV septum).

A chest X-Ray will be taken after the procedure to ensure the pacemaker leads are in position.

AV delay optimisation: will be performed using acute non-invasive blood pressure acquired using the Finometer device (Finapres Medical Systems, Netherlands). The BHF alternation protocol we have previously described will be used in order to minimise the effect of background noise ²².

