Appendix 2. Summary of study procedures/assessments by visit

‡ Visit at local hospital where patient was identified

^ Performed at Imperial College Healthcare NHS Trust

& Taken at screening visit or within the past 18 months

* RUM questionnaire only at visit 1, all questionnaires for visits 3-5

Either at local hospital or at Imperial College Healthcare NHS Trust £ Taken on the day or within the last 12 months

\$ Taken on the day of implantation or within the past 30 days

+ Taken at screening visit or within the past 18 months for patients with EF 36-40%

	Screening [*]	Implantation [#]	Randomisation [^]	Cross-over^	End of Study [^]
Visit	1	2	3	4	5
Month/Week/Day	- 2 to 6 months	-2 months (± 14 days)	0	6 months (± 14 days)	12 months (± 14 days)
Informed consent	Х				
Inclusion & exclusion criteria	Х				
Demography	Х				
Medical history	Х				
Vital signs	Х	Х	Х	Х	Х
Concomitant medication	Х				
Pregnancy test for women of child bearing age	Х				
Safety blood tests (Creatinine, Haemoglobin, PT, G+S)		X£			
ECG	X&	X\$			
Device Implantation		Х			
Post implantation chest radiograph		Х			
Pacing check			Х	Х	Х
Device programmed on/off			Х	Х	Х
CPET			Х	Х	Х
Echocardiography	X&		Х	Х	Х
BNP	X+		Х	Х	Х
QOL and Cost Effectiveness questionnaires (EQ5D-5L/MLHFQ and the HOPE-HF RUM)	X*		х	Х	Х
Haemodynamic optimisation			Х	Х	
Revelation of treatment sequence to patient					Х
His pacing on/off according to patient's choice (Patient can make decision later)					Х

Confidential

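### The only required pregnancy test is at screening, up to 4 months before the device is implanted, and none is required at the implantation visit

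*Protocol*

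**What the plan says.** Section 5.1, item 7, places the pregnancy test among the assessments of the screening visit: "Pregnancy test will be performed for women of childbearing age". Appendix 2 agrees. Its row "Pregnancy test for women of child bearing age" has a single mark, in the visit 1 column.

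Section 5.3 sets the latest time for implantation: "no later than 4 months of the patient's screening visit". In Appendix 2, screening falls 2 to 6 months before randomisation, and implantation is placed before randomisation by "2 months (± 14 days").

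The tests required before the procedure are set out in three places, none of which includes a pregnancy test:

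- Section 5.3: "Prior to implantation, blood tests will be performed to assess clotting function, full blood count and electrolytes".
- Section 5.3, a few lines on: "the following routine blood tests will be performed: creatinine level, haemoglobin level, prothrombin time (PT; clotting), and Group and Save (G+S").
- Appendix 2, visit 2 column: "Safety blood tests (Creatinine, Haemoglobin, PT, G+S").

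The eligibility row of Appendix 2, "Inclusion & exclusion criteria", is also marked at visit 1 only. Exclusion criterion 6 in section 4.1 makes pregnancy an exclusion and asks for a negative test before randomisation. Randomisation comes two months after implantation (section 5.4).

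**The concern.** Fetal exposure would occur at implantation. The procedure uses fluoroscopy (its duration is reported under sections 2.4 and 8.2), sedation may be given, and a chest X-ray follows (section 5.3). The protocol's one test can precede all this by months, and the event to which criterion 6 ties the negative result comes after it.

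The screening test does exclude women already pregnant at screening. It cannot detect a conception between screening and implantation. If the woman is unaware of the pregnancy, no step in the protocol would reveal it before she is exposed.

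For some participants the exposure comes from the trial itself. Section 1.3 says this population has no bradycardia indication for pacing, and group A in section 4.1 has no ICD indication either. For these women the trial should require the check.

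**Working it through.** **Inputs**

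- Screening: 2 to 6 months before randomisation (Appendix 2).
- Implantation: 2 months before randomisation, ± 14 days (Appendix 2).
- Cap on the time from screening to implantation: 4 months (section 5.3).
- Length of a month: 30.4 days, used for conversion only.

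**Age of the test at implantation**

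1. Shortest nominal gap: 2 − 2 = 0 months.
2. Longest nominal gap: 6 − 2 = 4 months. This reproduces the section 5.3 cap, so text and table agree.
3. In days: 4 × 30.4 = 121.6, about 122 days.
4. The ± 14 days at visit 2 would by itself allow 122 + 14 = 136 days, but the section 5.3 cap holds the maximum at about 122.

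The range is therefore 0 to about 122 days. The protocol gives no typical interval.

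**Required pregnancy tests by visit (section 5.1 and Appendix 2)**

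| Visit | 1 Screening | 2 Implantation | 3 Randomisation | 4 Cross-over | 5 End of study |
|---|---|---|---|---|---|
| Tests | 1 | 0 | 0 | 0 | 0 |

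**Does criterion 6 add a second test?** No. A negative result at screening is a negative result before randomisation, so the visit 1 test satisfies the criterion. The criterion and the schedule are consistent with each other, but neither calls for a test near the procedure.

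**Does another visit 2 step cover it?** No. The named tests are clotting, full blood count, electrolytes, creatinine, haemoglobin and group and save. The eligibility check is not repeated at visit 2.

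**Effect of the proposed change.** With a test at most 3 days before implantation (a proposed value, not one from the protocol), the maximum test age falls from about 122 days to 3 days.

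**The case against.** The strongest reply is that nothing in the protocol is contradictory. Pregnancy is an exclusion, a test is scheduled, and a pregnancy recognised before implantation would bar the woman. What remains needs four things together: a woman of childbearing age, conception between screening and implantation, no awareness of it, and no check by the hospital. The protocol offers no basis for estimating how often that would happen, and 122 days is a ceiling rather than a typical gap. Section 5.3 leaves part of the care around the procedure to local policy, and section 1.2 refers to detailed implantation guidance that the protocol only summarises. Either might provide for a pregnancy test.

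Most of this stands, and it keeps the point minor. It does not close the gap. Where section 5.3 defers to local practice it names what is deferred (antibiotics, analgesia, sedation, and group and save), and pregnancy testing is not named. Implantation may be done at the local hospital or at the lead site, and the protocol sets no common rule on pregnancy testing for them.

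A second objection concerns the remedy. If criterion 6 were changed only to ask for a negative test before implantation, a 4-month-old screening test would still satisfy it. That is correct. The edit has force only alongside a visit 2 test with a stated window.

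**Conclusion.** The concern holds as a minor safety improvement. It is not an inconsistency in the protocol. The single required pregnancy test can be up to about 122 days old at implantation, and no repeat is required before fluoroscopy, possible sedation and a chest X-ray.

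Two matters bear on the expected harm, and the protocol settles neither: how many women of childbearing age will enrol (assumed few), and whether implanting hospitals already test routinely. If they do, the practical risk is smaller still. The primary endpoint, sample size, power and analysis are not affected.

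**What to change.** 1. In Appendix 2, add a pregnancy test for women of childbearing age to the visit 2 column, on the day of implantation or within a short stated window before it. Three days is offered as an example, and the sponsor may choose another short limit. Appendix 2 already uses footnotes to set how old a visit 2 test may be (30 days for the ECG), so the format exists.
2. In section 5.3, name the pregnancy test among the pre-implantation tests.
3. In section 4.1, reword exclusion criterion 6 to require a negative result before device implantation, and refer to the visit 2 test so that an old screening result does not suffice. A positive result then excludes the woman before the procedure.
4. Keep the screening test, which spares women already pregnant from going further.

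The cost is one table entry with its window, one item in a list and one reworded phrase. In practice it adds one simple test for what are probably few women, at a visit where other pre-implantation results are already needed. Nothing in the analysis changes.

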5.2 Visit Schedule

A summary of study procedures/assessments by visit is presented in table 1.

Patients will be screened at participating hospitals and have implantation performed at the participating hospital or at the lead research site - Hammersmith Hospital, which is Imperial

Confidential

College Healthcare NHS Trust. Two months after patients are implanted with their device, patients will attend 3 more study visits at Imperial College Healthcare NHS Trust. Patients coming from other hospitals will be registered with the Hammersmith Hospital for study visits.

5.3 Treatment

Patients entering the study will then attend for implantation of their device, this will be performed either at their local hospital or at Imperial College NHS Healthcare Trust, no later than 4 months of the patient's screening visit

Prior to implantation, blood tests will be performed to assess clotting function, full blood count and electrolytes. Additionally, blood will be taken for group and save if required as per local clinical practice. Antibiotic prophylaxis, analgesia and sedation can all be given as per the implanting institution's local policies and normal practice. As is standard clinical practice for pacemaker implantation, the following routine blood tests will be performed: creatinine level, haemoglobin level, prothrombin time (PT; clotting), and Group and Save (G+S). Tests performed up to a specified date prior to the implantation day can be accepted, please refer to Appendix 2 for details.

All patients will be implanted with a Pacemaker or Implantable cardioverter defibrillator (ICD). In all patients, a pacing lead will be positioned in the right atrium (typically the right atrial appendage). All patients will have a pacemaker lead positioned on the His bundle in order to obtain His-bundle capture. If it is not possible to successfully implant a His-bundle lead with selective His bundle capture or non-selective capture with < 40ms prolongation of the QRS duration, then a lead will be implanted in a lateral branch of the coronary sinus.

In patients who do not have an indication for an Implantable cardioverter defibrillator (ICD), a second ventricular lead will be implanted in a lateral branch of the coronary sinus. If His pacing has not been successfully achieved then a further lead will be positioned at the RV apex. In patients who do have an indication for an Implantable cardioverter defibrillator, the ICD lead will be positioned in the right ventricle (either RV apex or RV septum).

A chest X-Ray will be taken after the procedure to ensure the pacemaker leads are in position.

AV delay optimisation: will be performed using acute non-invasive blood pressure acquired using the Finometer device (Finapres Medical Systems, Netherlands). The BHF alternation protocol we have previously described will be used in order to minimise the effect of background noise ²².

The optimal AV delay will be determined during atrial sensing and atrial pacing. For atrial pacing the optimisation will be performed at 10-20 bpm above the resting heart rate provided AV conduction is 1:1 during AAI pacing at this heart rate. If Wenkebach conduction or heart block occurs at this rate then we will lower heart rate in order to achieve 1:1 conduction. If 1:1 conduction is not achievable at the lower heart rate, then the paced AV delay optimisation will be performed with a reference setting of His pacing with an AV delay of 120ms.

For atrial sensing, optimisation will be performed at resting heart rate.

After implantation of the device, there will be a 2 month run-in period prior to randomisation, the device will be programmed not to deliver His pacing therapy during this period.

5.4 Randomisation and Crossover

Two months after patients are implanted with their device, patients will be randomised to either receive active His pacing treatment or no His pacing treatment (e.g. pacemaker programmed to VVI or DDD/I 30 bpm). After a further 6 months, they will be crossed over to the alternative treatment arm. Treatment allocation will be obtained using an Interactive Web Response System (IWRS) programmed with a randomisation schedule provided by the trial statistician. Appropriate blocking will be used.

The patient will have study assessments listed in table 1 and described in the section 5.5.

The physiologists performing study tests will be blinded to the treatment arm. A separate investigator will be responsible for programming the device.

5.5 Study assessments

Physical examination

Patients will have a physical examination where vital signs will be taken.

Cardiopulmonary exercise testing:

Patients will exercise on a treadmill using a "smoothed modified Bruce" protocol ³⁰. A physiologist and another HOPE HF study team member (e.g. research nurse, research fellow or another physiologist) will be present for this test. For safety reasons, it is necessary to perform ECG monitoring during this test. It may be possible to see pacing spikes in the ECG. Therefore to ensure that the physiologist who is leading the exercise test is blinded, the screen displaying the ECG will only be visible to the second study personnel who will be responsible for monitoring ECG. They will only request that a test is stopped if there are ECG findings which make this necessary on clinical safety grounds. This way both the patient and the physiologist leading the exercise test will remain blinded to the treatment arm. Exercise capacity will be measured as peak exercise oxygen consumption in ml/kg/min.

BNP:

We will take 5mls of blood to measure B type Natriuretic Peptide (BNP) in an EDTA bottle. The samples will be analysed at the Hammersmith hospital and no sample will be stored.

Echocardiography:

Patients will have a standard HOPE HF echo protocol performed including left ventricular dimensions, volumes, ejection fraction and quantification of mitral regurgitation. No ECG will be recorded during the echocardiogram once the patient is randomised. The physiologist performing the test will be blinded to the treatment arm.

Daily Activity Measurement:

All implanted devices in the study can provide data on daily activity measured in minutes per day. The comparison will be made between the His pacing and no His pacing arms.

Quality of Life (QOL) and Cost Effectiveness Evaluation questionnaires:

The economic evaluation will compare incremental costs and incremental outcomes of the direct His-bundle pacing against standard medical care. The economic evaluation will consist of two parts, a cost-effectiveness analysis (CEA) and a cost utility analysis (CUA). In the CEA the incremental cost-effectiveness ratio (ICER) will be expressed as the incremental costs per point improvement in exercise capacity in peak VO₂. The primary outcome measure in the CUA will be Qualitative Adjusted Life Years (QALYs), based on the EuroQoL EQ-5D scores.

In order to measure the costs of the resources patients use, a resource use measurement (RUM) questionnaire will be developed and validated for the HOPE-HF study. The RUM questionnaire consists of a standard RUM questionnaire with small adaptations specific to the subject of heart failure patients.

We will use the Minnesota Living with Heart Failure Questionnaire (MLHFQ) (http://www.mlhfq.org/) and EQ-5D to assess for changes in quality of life (QoL). The MLHFQ questionnaire is a validated condition-specific measure with good sensitivity and discrimination. It will be complemented with the EuroQoL EQ-5D both of these are well validated generic measures of QoL.

The trial staff administering these questionnaires will be blinded to the treatment arm.

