If selective His bundle pacing cannot be achieved then non-selective His bundle pacing will be accepted. Non-selective His pacing is defined as the direct capture of the basal ventricular myocardium in addition to His bundle capture.

Patients will be randomised to 6 months of the following:

1) *Active treatment*: His bundle pacing with the AV delay programmed to the optimal sensed and paced delays identified during the optimisation process

2) *No His pacing treatment:* pacemaker programmed to avoid pacing as per the implanting physicians discretion utilising the non His ventricular lead (suggested modes are VVI 30, DDD/I 30 etc). His pacing should only be programmed on active treatment.

Dynamic AV delay will be programmed off throughout the study.

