1.3 Risk / Benefit Assessment

The risks associated with pacemaker implantation include:

- ~1% of developing pneumothorax
- ~1% of infection of pacemaker
- ~1% of lead displacement or device malfunction
- < 1% risk of pericardial effusion
- ~ 3% risk of haematoma
- ~2% risk of access vein clot

In order to minimise these risks, procedures will be carried out by highly experienced, high volume pacemaker implanters. All procedures will be carried out in centres which have the facilities and expertise available to manage complications should they occur.

Potential benefits of pacing in this population

- Improvement in heart failure symptoms
- Prevention of bradycardia (while this population do not have a pacing indication for bradycardia they are at increased risk of developing higher degrees of conduction

block or sinus bradycardia). The pacemaker will prevent bradycardia from occurring and symptoms occurring as a result of this.

• Patients with prolonged PR interval and heart failure are at higher risk of adverse outcomes including death. While this study is not powered to assess for a mortality benefit it is possible that the risk of death will be reduced with pacing therapy.

The Data Monitoring Committee will meet regularly and will review adverse event rates. If they are found to be higher than expected then appropriate action will be taken.

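### Section 5.5 names standard medical care as the economic comparator, but the trial only compares His pacing on with His pacing off in patients who all have the implant

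*Protocol*

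**What the plan says.** Cost effectiveness is a named secondary endpoint: section 2.4, item 5, lists "Cost effectiveness analysis". Section 5.5 sets the comparison: "The economic evaluation will compare incremental costs and incremental outcomes of the direct His-bundle pacing against standard medical care". The effect measures are peak VO₂ for the cost-effectiveness analysis and QALYs from EQ-5D for the cost-utility analysis.

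The design sections describe a different contrast. Section 3.1: "All patients will be implanted with a Pacemaker or Implantable Cardioverter Defibrillator with one of the leads positioned on the His bundle". Section 5.3 places a two-month run-in between implant and randomisation. Section 5.4 randomises patients to His pacing or no His pacing and then crosses them over. Section 1.2 describes the control state as a "pacemaker programmed to avoid pacing as per the implanting physicians discretion utilising the non His ventricular lead". For daily activity, section 5.5 itself names this contrast: "The comparison will be made between the His pacing and no His pacing arms".

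Section 8.2(iii) defines the ICER as the cost difference divided by the effect difference between the intervention and control groups.

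**The concern.** Sections 5.5 and 8.2(iii) describe two different quantities under one name. The first is the value of offering the implant and pacing to a patient on standard care. The second is the value of turning His pacing on once the device is in place. A payer deciding whether to fund implantation needs the first; the trial observes only the second.

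Reported under the section 5.5 label, the on-versus-off ICER would be read as an answer to the funding question. On the cost side it would leave out the incremental cost of the device, leads and procedure, which makes it look more favourable when the effect is positive. On the effect side it would leave out whatever the implanted system does in both states. That includes the procedural risks listed in section 1.3 and, so far as it is the same in both states, the benefit claimed there: "The pacemaker will prevent bradycardia from occurring and symptoms occurring as a result of this".

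**Working it through.** **The plan's own figures.** The protocol gives no cost and no ICER, so there is no economic figure to reproduce. The nearest figure is the sample size in section 8.1. A paired t-test with difference 0.7, SD 2.4, two-sided alpha 0.05 and power 90% gives n = 126 (power 0.901), and 126 / (1 − 0.21) = 159.5, rounded up to 160. Both agree with the protocol. The present point does not depend on them; it only borrows the effect sizes 0.7 and 0.9 ml/kg/min.

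**Step 1. What differs between the two states.**

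| Item | His pacing on | His pacing off | Standard medical care |
|---|---|---|---|
| Device, leads and implant procedure | yes | yes | not observed |
| AV-optimised His pacing | yes | no | not observed |
| Randomised period in the trial | 6 months | 6 months | none |

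Because of the crossover, the same patients supply both observed columns, so an implant cost incurred before randomisation is identical in the two.

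**Step 2. Whether pre-implant data could stand in for standard care.** From Appendix 2, with implant at visit 2:

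- Peak VO₂ (CPET): visits 3, 4, 5, so 0 of 3 before implant.
- EQ-5D: visits 3, 4, 5, so 0 of 3 before implant.
- Resource-use questionnaire: visits 1, 3, 4, 5, so 1 of 4 before implant.

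Neither effect measure is observed before implant. The baseline adjustment in section 8.2(iii) deals with differences between groups, so it cannot restore a cost that both share.

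**Step 3. Cost side.** Write ΔC and ΔE for the on-minus-off differences in cost and effect. Let C be the average incremental implant cost per patient relative to standard care, and d the effect of the implanted device with His pacing off relative to standard care. The documents give neither C nor d.

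- Planned ICER: ΔC / ΔE
- ICER against standard care: (ΔC + C) / (ΔE + d)

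With d = 0 the two differ by C / ΔE:

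- at the 0.7 ml/kg/min used for sample size: C / 0.7 = 1.43 × C per ml/kg/min
- at the expected 0.9 ml/kg/min: C / 0.9 = 1.11 × C per ml/kg/min

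For scale only, with assumed values of C in arbitrary currency units:

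| Assumed C | Shift at 0.7 | Shift at 0.9 |
|---|---|---|
| 2,000 | 2,857 | 2,222 |
| 5,000 | 7,143 | 5,556 |
| 10,000 | 14,286 | 11,111 |

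**Step 4. Direction when d is not zero.** Take ΔE > 0 and ΔE + d > 0. The standard-care ICER exceeds the planned one when (ΔC + C) × ΔE > ΔC × (ΔE + d). This reduces to C × ΔE > d × ΔC, that is, C > d × (ΔC / ΔE). The planned ICER is the more favourable of the two only under that condition, and the documents do not settle whether it is met.

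**Step 5. Who is most affected.** Section 4.1 separates "patients who do not have an indication for an implantable ICD (this group will receive His CRT-P") from "patients who do have an indication for an implantable ICD (this cohort will receive His CRT-D"). For the first group, up to the full CRT-P implant cost is left out. For the second, if standard care would itself provide an ICD, only the excess of the His CRT-D system over an ICD is left out. Section 8.2(iv), item 8, expects most patients by far to be in the second group, so the average C is smaller than a full implant cost.

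**The case against.** The strongest reply is that this is one loose phrase in a section on questionnaires. The operative definition is in section 8.2(iii), and a statistician following it would compute on versus off. On that reading, standard medical care is shorthand for the control period. The reading fits poorly: section 2.1 describes the population as one that pacing for heart failure does not currently target, yet every control-period patient carries a CRT device. If it is what was meant, the wording still needs the same correction.

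A second reply is that cost items, attribution and modelling usually belong in the analysis plan, which is not shown and could add device costs. That is fair, and the loss of implant cost is therefore conditional on it. But the protocol itself names the comparator and defines the ICER, and the two disagree whatever another document adds.

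Third, the size is unknown, the direction is open, and the gap is smaller for patients with an ICD indication. All of this stands and limits the weight of the point. The multiples 1.43 and 1.11 are simply reciprocals of the assumed effects.

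Fourth, equal bradycardia protection in both states is not shown. The suggested control modes provide backup at 30 bpm, and the protocol does not give the lower rate in the active state. This too stands: bradycardia prevention cancels only so far as it is equal, and the conclusion does not rest on it.

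**Conclusion.** The point holds. As written, section 5.5 promises a comparison that the design does not contain, and section 8.2(iii) computes a different one. The mismatch follows from the protocol's own text with no outside assumption.

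Its numerical consequence is conditional. If implant costs are not added separately and the device with His pacing off has no effect relative to standard care, the reported cost per ml/kg/min is too low for a standard-care reading by 1.11 to 1.43 times the average incremental implant cost. With a non-zero device effect the direction depends on C and d. The primary endpoint, its analysis and the sample size are unaffected. The correction should be made because it changes what a named secondary endpoint can be said to show.

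**What to change.** In sections 5.5 and 8.2(iii), restate the within-trial comparator as AV-optimised His pacing on versus no His pacing in implanted patients, and state that the resulting ICER will not be reported as a comparison with standard medical care. If the sponsor wishes to keep a standard-care comparison, describe it as a separate modelled analysis and say how incremental implant costs and effects enter it, including what standard care is taken to be for patients with and without an ICD indication.

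The correction is wording only and needs no new data, visits or patients. Its price is a narrower economic conclusion from the trial itself. A standard-care analysis, if kept, would rest partly on assumptions from outside the trial and should be presented that way.
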